1.1 Title

Saxagliptin and Cardiovascular Outcomes in Patients with Type 2 Diabetes Mellitus ([SAVOR- TIMI 53 trial](#))

1.2 Intended aim(s)

The cardiovascular safety and efficacy of many current antihyperglycemic agents, including saxagliptin, a dipeptidyl peptidase 4 (DPP-4) inhibitor, are unclear. This trial was designed to evaluate the safety and efficacy of saxagliptin with respect to cardiovascular outcomes in patients with diabetes mellitus who are at risk for cardiovascular events.

1.3 Primary endpoint for replication and RCT finding

Composite of CV death, nonfatal myocardial infarction, or nonfatal ischemic stroke

1.4 Required power for primary endpoint and noninferiority margin (if applicable)

85% power to identify a 17% relative reduction of the primary end point with saxagliptin versus placebo and 98% power to test for noninferiority of saxagliptin versus placebo (reject the upper limit of 95% CI for an HR 1.3 at a 1-sided α of .025)

1.5 Primary trial estimate targeted for replication

HR = 1.00 (95% CI 0.89-1.12) comparing saxagliptin to placebo (Scirica et al., 2013)

2. Person responsible for implementation of replication in Aetion

[name]. implemented the study design in the Aetion Evidence Platform. S/he is not responsible for the validity of the design and analytic choices. All implementation steps are recorded and the implementation history is archived in the platform.

[figure not shown]
3. Data Source(s)

United/Optum, MarketScan, Medicare

4. Study Design Diagram

The study design diagram visualizes key aspects of the longitudinal study design for expedited review.

Design Diagram – SAVOR-TIMI 53 TRIAL REPLICATION

5. Cohort Identification

5.1 Cohort Summary

This study will involve a new user, parallel group, cohort study design comparing saxagliptin to the 2nd generation sulfonylurea (SU) antidiabetic class as a proxy for placebo. 2nd generation SUs are not known to have an impact on the outcome of interest. In addition, SUs were the most frequent background treatment in SAVOR-TIMI53 (after metformin), and DPP4i and SUs are preferentially prescribed to similarly older patients in real world (Patorno et al., 2019). The patients will be required to have continuous enrollment during the baseline period of 180 days before initiation of saxagliptin or a comparator drug (cohort entry date). Follow-up for the outcome (3P-MACE), begins the day after drug initiation. As in the trial, patients are allowed to take other antidiabetic medications during the study

5.2 Important steps for cohort formation

5.2.1 Eligible cohort entry dates

Market availability of saxagliptin in the U.S. started on July 31, 2009

- For Marketscan: July 31, 2009-Dec 31, 2017 (end of data availability).
- For Medicare: Jan 1, 2012-Dec 31, 2017 (start- end of data availability).
- For Optum: July 31, 2009-March 31, 2019 (end of data availability).

5.2.2 Specify inclusion/exclusion criteria for cohort entry and define the index date

Inclusion and exclusion criteria were adapted from the trial as closely as possible. Definitions for all inclusion/exclusion are provided in **Appendix A** and are summarized in the flowcharts below.

5.3 Flowchart of the study cohort assembly

	Optum	Truven	Medicare

	Less Excluded Patients	Remaining Patients	Less Excluded Patients	Remaining Patients	Less Excluded Patients	Remaining Patients
All patients in the database		74,864,884		191,990,035		23,466,175
Patients who used exposure or a reference between 20 January 2010 to Dec 2017 (for Marketscan)/March 2019 (for Optum) and 01 January 2012-December 2017 for Medicare	-73,333,681	1,531,203	-189,850,391	2,139,644	-20,002,243	3,463,932
Patients who have continuous 6 months registration in the database	-198,718	1,332,485	-233,411	1,906,233	-926,605	2,537,327
Patients without prior use of reference	-837,680	494,805	-1,282,498	623,735	-1,516,234	1,021,093
Patients without prior use of exposure	-58,834	435,971	-71,555	552,180	-57,547	963,546
Excluded because patient qualified in >1 exposure category	-193	435,778	-301	551,879	-111	963,435
Patients who did not have missing age information	-13	435,765	0	551,879	0	963,435
Patients who did not have missing gender information	-26	435,739	0	551,879	0	963,435
Excluded based on Inclusion 1- DM Type 2	-20,512	415,227	-49,327	502,552	-8,942	954,493
Excluded based on Inclusion 2- Age >=40	-8,101	407,126	-17,260	485,292	0	954,493
Excluded based on Inclusion 4- High risk for a CV event defined as having either established CV disease and/or multiple risk factors	-34,138	372,988	-73,801	411,491	-3,577	950,916
Excluded based on Exclusion1- CCI >=10	-3,466	369,522	-1,659	409,832	-17,277	933,639
Excluded based on Exclusion 2- treatment with an incretin-based therapy such as DPP-4 inhibitors and/or GLP-1 mimetics	-13,198	356,324	-18,748	391,084	-33,418	900,221
Excluded based on Exclusion 3- Acute vascular (cardiac or stroke) event <2 months [i.e. ACS/unstable angina OR Any stroke (inpatient, any)]	-766	355,558	-1,546	389,538	-1,979	898,242
Excluded based on Exclusion 4- chronic dialysis or renal transplant	-592	354,966	-434	389,104	-2,718	895,524
Excluded based on Exclusion 5- Pregnancy	-7	354,959	-11	389,093	-9	895,515
Excluded based on Exclusion 6- HIV/AIDS (dx and meds) with ICD10 CODES	-129	354,830	-104	388,989	-206	895,309
Excluded based on Exclusion 7- Lupus	-174	354,656	-122	388,867	-517	894,792
Excluded based on Exclusion 8- long-term (>30 consecutive days) oral corticosteroids use	-2,286	352,370	-2,495	386,372	-7,501	887,291
Excluded based on Exclusion 9- Morbid Obesity	-3,600	348,770	-2,126	384,246	-6,087	881,204
Excluded based on Exclusion 13- Non-compliance	-1408	347,362	-447	383,799	-2,954	878,250

Final cohort	347,362	383,799	878,250
--------------	---------	---------	---------

* Medicare database includes only patients with at least one diagnosis for diabetes, heart failure, or cerebrovascular disease.

6. Variables

6.1 Exposure-related variables:

Study drug:

The study exposure of interest is initiation of saxagliptin. Initiation will be defined by no use of saxagliptin or a comparator in the prior 6 months before treatment initiation (washout period).

Comparator agents:

- Initiators of saxagliptin will be compared to initiators of-
 - 2nd generation sulfonylureas

Because saxagliptin and comparators are frequently used as second or third line treatments of T2DM, we expect it to be unlikely that saxagliptin and comparators are initiated in patients with substantially different baseline risk for proposed outcomes.

6.2 Preliminary covariates:

- Age
- Sex
- Combined Comorbidity Index (CCI), measured over the default baseline covariate assessment period, defined as 180 days prior to and including index date

Covariates listed above represent only a small subset of covariates that will ultimately be controlled for in the design and analysis. We use the covariates above only for initial feasibility analyses to judge whether there is likely to be sufficient overlap between treatment groups to proceed with the study. Remaining covariates are defined only after the study has passed the initial feasibility analysis and the initial power assessment and are listed in Table 1 (**Appendix B**). These covariates are based on those used by Patorno et al. (2019).

6.3 Outcome variables and study follow-up:

6.3.1 Outcome variables

Effectiveness outcomes of interest (definitions provided in **Appendix A**):

- **Primary outcome:** 3-point major adverse cardiovascular events (MACE), i.e., non-fatal myocardial infarction, non-fatal stroke, or CV mortality
- Secondary outcomes: Individual MACE components:
 - Hospital admission for MI (for purposes of this individual component, fatal MI is included)
 - Hospital admission for stroke (for purposes of this individual component, fatal stroke is included)
 - All-cause mortality/CV mortality:
 - All-cause inpatient mortality identified using discharge status codes will be used as a proxy for "CV mortality" in commercial databases
 - Information on CV mortality through data linkage with the National Death Index (NDI) will only become available at a later date for Medicare and will be used in secondary analyses.

Control outcomes of interest (control outcomes only serve to assess aspects of study validity but are not further interpreted):

1. Severe hypoglycemia (we expect to see protective effect; American Diabetes Association, 2018)

Control outcome definitions

Outcome	Hospital Discharge Code(s)	Comments
Severe hypoglycemia	Severe hypoglycemia Any-position ED or primary inpatient ICD-9 diagnosis: 251.0, 251.1x, 251.2x, or 250.8x. Outcomes identified by 250.8x are not included if they co-occur with one of the following diagnoses: 259.8, 272.7, 681.xx, 682.xx, 686.9, 707.1x, 707.2x, 707.8, 707.9, 709.3, 730.0x, 730.1x, 730.2x, 731.8	Note- The corresponding ICD-10 codes will be used also

6.3.2 Study follow-up

Both as-treated (AT) and intention-to-treat (ITT) analyses will be conducted with treatment defined as the index drug on the day of cohort entry. Because adherence in the real world databases is expected to be much worse than in the trial, the AT analysis is the **primary** analysis, as it targets the relative hazard of outcomes on treatment.

For the AT analyses, the follow-up will start the day after initiation of liraglutide and comparator and will continue until the earliest date of the following events:

- The first occurrence of the outcome of interest, unless otherwise specified for selected outcomes,
- The date of end of continuous registration in the database,
- End of the study period,
- Measured death event occurs,
- Nursing home admission
 - Nursing home admissions are considered a censoring event because the data sources utilized typically provide little to no data on a patient, particularly on drug utilization, after admission. We will utilize this as an exclusion reason for cohorts for the same reason.
- The date of drug discontinuation, defined as the date of the last continuous treatment episode of the index drug (saxagliptin and comparator) plus a defined grace period (i.e., 30 days after the end of the last prescription's days' supply in main analyses).
- The date of augmentation or switching from an exposure to a comparator or any other agent in the comparator class and vice versa (e.g. switching from glimepiride to glipizide would be a censoring event);
 - A dosage change on the index treatment does not fulfill this criterion
 - An added treatment that is not part of the exposure or comparator group does not fulfill this criterion (e.g. if a saxagliptin user adds insulin, he or she does not get censored at the time of insulin augmentation)

For the ITT analyses, the censoring based on the augmentation/switching and treatment discontinuation will be replaced with a maximum allowed follow-up time of 365 days.

7. Initial Feasibility Analysis

Action report links:

Optum- <https://bwh-dope.aetion.com/#/projects/details/641/results/29994/result/0>

Marketscan- <https://bwh-dope.aetion.com/#/projects/details/642/results/29995/result/0>

Medicare- <https://bwh-dope.aetion.com/#/projects/details/643/results/29996/result/0>

Date conducted: rerun on 01/07/2019

Complete Action feasibility analysis using age, sex, and CCI as the only covariates and the primary endpoint (Section 6.3.1) as the outcome. No measures of association will be computed nor will incidence rates stratified by treatment group.

- Report patient characteristics by treatment group
- Report summary parameters of the overall study population
- Report median follow-up time by treatment group
- Report reasons for censoring in the overall study population

8. Initial Power Assessment

Action report links:

Optum- <https://bwh-dope.aetion.com/#/projects/details/641/results/29997/result/1>

Marketscan- <https://bwh-dope.aetion.com/#/projects/details/642/results/29998/result/1>

Medicare- <https://bwh-dope.aetion.com/#/projects/details/643/results/29999/result/1>

Date conducted: rerun on 01/07/2019

- In order to complete the initial power analysis, the dummy outcome of a 90-day gap in database enrollment will be used. This outcome is used to ensure that no information on the comparative risks of the outcomes of interest are available at this stage. Complete a 1:1 PS-matched comparative analysis using this outcome. PS should include only 3 covariates: age, sex, and combined comorbidity index. Power calculations are based on the formulas from Chow et al. (2008).
- Stop analyses until feasibility and power are reviewed by primary investigators and FDA. Reviewers evaluate the results of the analyses described above in Sections 7 and 8, including numbers of patients, patient characteristics, follow-up time, and reasons for censoring by treatment group, as well as overall rates of outcomes and study power. These parameters are re-evaluated and reported in the subsequent sections, after incorporating feedback and refining the protocol.

Reviewed by PI:	[name]	Date reviewed:	10/26/18
Reviewed by FDA:	[name]	Date reviewed:	12/19/18
Reasons for stopping analysis (if required):			

9. Balance Assessment after PS matching

Action report name:

Optum- <https://bwh-dope.aetion.com/projects/details/641/results/44771/result/0>

Marketscan- <https://bwh-dope.aetion.com/projects/details/642/results/44772/result/0>

Medicare- <https://bwh-dope.aetion.com/projects/details/643/results/45431/result/0>

Date conducted: 11/18/2019 (Medicare 11/30/2019)

After review of initial feasibility and power analyses, complete creation of the remaining covariates (see Table 1 below for list of covariates). Again, using the dummy outcome of a 90-day gap in database enrollment, complete a 1:1 PS-matched analysis. The PS should include the complete list of covariates (excluding laboratory values, which are missing in some patients).

- Provide plot of PS distributions stratified by treatment group.

Note- Please refer to **Appendix B**.

- Report covariate balance after matching.

Note- For Table 1, please refer to **Appendix B**.

- Report reasons for censoring by treatment group.

	Overall	Referent	Exposure
Dummy Outcome	0 (0.00%)	0 (0.00%)	0 (0.00%)
Death	1,783 (0.98%)	1,051 (1.15%)	732 (0.80%)
Start of an additional exposure	10,211 (5.61%)	976 (1.07%)	9,235 (10.14%)
End of index exposure	122,449 (67.23%)	61,560 (67.60%)	60,889 (66.86%)
Specified date reached	11,855 (6.51%)	7,184 (7.89%)	4,671 (5.13%)
End of patient enrollment	25,411 (13.95%)	13,085 (14.37%)	12,326 (13.54%)

Switch to other SUs (for censoring) + nursing home admission	10,419 (5.72%)	7,208 (7.92%)	3,211 (3.53%)
--	----------------	---------------	---------------

- Report follow-up time by treatment group.

Patient Group	Median Follow-Up Time (Days) [IQR]		
	Optum	Marketscan	Medicare
Overall Patient Population	139 [58-344]	153 [82-367]	155 [85-373]
Referent	144 [78-354]	180 [102-432]	180 [102-432]
Exposure	132 [58-331]	140 [58-323]	140 [58-323]

- Report overall risk of the primary outcome.

	Optum	Marketscan	Medicare
Risk per 1,000 patients	13.68	16.21	38.38

10. Final Power Assessment

Date conducted: 2/1/2019

- Re-calculate power in the appropriate excel table, using the revised number of matched patients from the PS-match in Section 9. All other parameters in the table should be the same as in Section 8. If the study is to be implemented in more than one database, copy and paste excel sheet to report power for each database separately and for the pooled analysis that uses data from all databases together. Power calculations are based on the formulas from Chow et al. (2008).
 - Pooled

Non-inferiority Analysis		Superiority Analysis	
Number of patients matched		Number of patients matched	
Reference	91,063	Reference	91,063
Exposed	91,063	Exposed	91,063
Risk per 1,000 patients	22.76	Risk per 1,000 patients	22.76
Assumed HR from RCT	1	Desired HR from RCT	0.83
Alpha (2-sided)	0.05	Alpha (2-sided)	0.05
Non-inferiority margin	1.3		
Number of events expected	4145.18776	Number of events expected	4145.18776
Power	1	Power	0.999973077

- Optum

Non-inferiority Analysis		Superiority Analysis	
Number of patients matched		Number of patients matched	
Reference	20,772	Reference	20,772
Exposed	20,772	Exposed	20,772
Risk per 1,000 patients	13.68	Risk per 1,000 patients	13.68
Assumed HR from RCT	1	Desired HR from RCT	0.83
Alpha (2-sided)	0.05	Alpha (2-sided)	0.05
Non-inferiority margin	1.3		
Number of events expected	568.32192	Number of events expected	568.32192
Power	0.878466057	Power	0.602983034

- Marketscan

Non-inferiority Analysis		Superiority Analysis	
Number of patients matched		Number of patients matched	
Reference	29,150	Reference	29,150
Exposed	29,150	Exposed	29,150
Risk per 1,000 patients	16.21	Risk per 1,000 patients	16.21
Assumed HR from RCT	1	Desired HR from RCT	0.83
Alpha (2-sided)	0.05	Alpha (2-sided)	0.05
Non-inferiority margin	1.3		
Number of events expected	945.043	Number of events expected	945.043
Power	0.980903542	Power	0.817020552

- Medicare

Non-inferiority Analysis		Superiority Analysis	
Number of patients matched		Number of patients matched	
Reference	41,141	Reference	41,141
Exposed	41,141	Exposed	41,141
Risk per 1,000 patients	38.38	Risk per 1,000 patients	38.38
Assumed HR from RCT	1	Desired HR from RCT	0.83
Alpha (2-sided)	0.05	Alpha (2-sided)	0.05
Non-inferiority margin	1.3		
Number of events expected	3157.98316	Number of events expected	3157.98316
Power	0.999999969	Power	0.999472659

- Stop analyses until balance and final power assessment are reviewed by primary investigators, FDA, and assigned members of advisory board. Reviewers evaluate the results of the analyses described above in Sections 9 and 10, including numbers of

patients, balance in patient characteristics, follow-up time, and reasons for censoring by treatment group, as well as overall rates of outcomes and study power.

Reviewed by PI:	[name]	Date reviewed:	12/9/19
Reviewed by FDA:	[name]	Date reviewed:	12/20/19
Reasons for stopping analysis (if required):			

11. Study Confidence and Concerns

Deadline for voting on study confidence and listing concerns: 12/20/19

- If final feasibility and power analyses are reviewed and approved, proceed to the remaining protocol steps.

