Appendix A

Mortality- Dependent on data source.

1. All-cause mortality / inpatient mortality

Identified using the vital status file-

Medicare

Identified using the discharge status codes-

Optum-

- 20 = EXPIRED
- 21 = EXPIRED TO BE DEFINED AT STATE LEVEL
- 22 = EXPIRED TO BE DEFINED AT STATE LEVEL
- 23 = EXPIRED TO BE DEFINED AT STATE LEVEL
- 24 = EXPIRED TO BE DEFINED AT STATE LEVEL
- 25 = EXPIRED TO BE DEFINED AT STATE LEVEL
- 26 = EXPIRED TO BE DEFINED AT STATE LEVEL
- 27 = EXPIRED TO BE DEFINED AT STATE LEVEL
- 28 = EXPIRED TO BE DEFINED AT STATE LEVEL
- 29 = EXPIRED TO BE DEFINED AT STATE LEVEL
- 40 = EXPIRED AT HOME (HOSPICE)
- 41 = EXPIRED IN A MEDICAL FACILITY (HOSPICE)
- 42 = EXPIRED - PLACE UNKNOWN (HOSPICE)

Truven-

- 20 - Died
- 22 - Died
- 23 - Died
- 24 - Died
- 25 - Died
- 26 - Died
- 27 - Died
- 28 - Died
- 29 - Died
- 40 - Other died status or Expired at home (Hospice claims only) (depends on year)
- 41 - Other died status or Expired in medical facility (Hospice claims only) (depends on year)

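### Nursing home admission still censors the Medicare ITT all-cause mortality analysis, discarding deaths that the vital status file records

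*Protocol*

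**What the plan says.** Section 6.3.2 reads the same in the Protocol and in the Combined protocol and SAP. It introduces a list of events that end follow-up in the AT analyses, and nursing home admission is one of them: "Nursing home admissions are considered a censoring event because the data sources utilized typically provide little to no data on a patient, particularly on drug" use, once the patient is there. It adds: "We will utilize this as an exclusion reason for cohorts for the same reason". The cohort flowchart in 5.3 has no such step.

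The ITT analyses are then defined by what changes: "the censoring based on the augmentation/switching and treatment discontinuation will be replaced with a maximum allowed follow-up time of 365 days". Nursing home admission is not mentioned there, and no exception is made by endpoint or database.

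Section 6.3.1 includes all-cause/CV mortality among the secondary outcomes. The mortality sheet in Appendix A gives the source of deaths by database. In Medicare they are "Identified using the vital status file"; in Optum and MarketScan (Truven) they come from discharge status codes. The Section 9 censoring table shows nursing home admission only inside a combined row, "Switch to other SUs (for censoring) + nursing home admission".

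**The concern.** An ITT analysis of death needs the date of entry, the drug started and the date of death. It does not need to know what was dispensed later. In Medicare the date of death does not depend on claims either. Take a Medicare patient who has a stroke, moves to a nursing home and dies three months later, within 365 days of entry. The vital status file holds that death, but the plan ends follow-up at admission and the mortality endpoint records no event.

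Cox regression treats such a patient as having, from then on, the same hazard as similar patients still under observation. That is doubtful for people who have just entered a nursing home. What is then estimated is the hazard of death among patients not admitted, rather than 365-day all-cause mortality by drug started. The population makes this more than a technicality. In the matched Medicare cohort (Appendix B, Table 1) mean age is about 74, and 65.3% of the SU arm and 64.8% of the saxagliptin arm are in the highest empirical frailty category.

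**Working it through.** **Step 1: does admission censor in ITT?** The ITT sentence names two kinds of censoring to be replaced, switching/augmentation and discontinuation. Replacing part of a list leaves the rest in force: outcome, end of enrollment, end of study period, death and nursing home admission.

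**Step 2: where does the stated reason apply?** The reason is a lack of patient data in general, and of drug data in particular.

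| Analysis | Needed after admission | Does the reason apply? |
|---|---|---|
| AT, any outcome | Dispensings, to know when treatment ends | Yes |
| ITT, MI or stroke | Hospital claims | It may |
| ITT, death in Optum or MarketScan | Discharge status on claims | It may |
| ITT, all-cause death in Medicare | Date of death in the vital status file | No |

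Only the last row lacks a justification.

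**Step 3: what do the counts show?** The inputs are from the Section 9 censoring table. They are pooled over the three databases, under AT follow-up with the dummy outcome. The denominators are 91,063 per arm and 182,126 in total. The stated percentages reproduce:

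- Combined row: 7,208/91,063 = 7.92% (SU), 3,211/91,063 = 3.53% (saxagliptin), 10,419/182,126 = 5.72% (overall).
- Deaths: 1,051/91,063 = 1.15% (SU), 732/91,063 = 0.80% (saxagliptin).

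The combined row is 7,208/1,051 = 6.9 times the deaths in the SU arm and 3,211/732 = 4.4 times those in the saxagliptin arm. So even a modest share of admissions in that row could matter, but the share is not reported.

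**Step 4: can size or direction be derived?** Two inputs are missing: the admissions by arm, and mortality after admission. As an illustration only, assume that 5% to 30% of those admitted die within the remaining window. The crude ratio of death counts, saxagliptin to SU, is 732/1,051 = 0.70 as tabulated.

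- If 3,211 are admitted in each arm: at 5%, (732 + 161)/(1,051 + 161) = 893/1,212 = 0.74; at 30%, (732 + 963)/(1,051 + 963) = 1,695/2,014 = 0.84.
- If the whole row is admissions in both arms: at 5%, (732 + 161)/(1,051 + 360) = 893/1,411 = 0.63; at 30%, (732 + 963)/(1,051 + 2,162) = 1,695/3,213 = 0.53.
- If no one in the row was admitted, it stays at 0.70.

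The ratio moves up in one scenario and down in the other. These are scenarios and not limits, they are ratios of counts and not hazard ratios, and they rest on pooled AT data, not on Medicare ITT data.

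**Step 5: power.** Lifting a censoring rule can only add events, so no power figure in Section 10 is reduced.

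**The case against.** The strongest reply is that the stated reason is wider than missing drug data. It speaks of little to no data on the patient, which also covers outcomes. That stands. A reader might infer that the reason fails for ITT as a whole, and the documents do not support this: MI and stroke need hospital claims, and deaths in Optum and MarketScan come from discharge codes.

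A reader might also extend the point to AT mortality. That does not hold. The AT analysis targets the hazard on treatment, so it needs dispensings to know when treatment ended. Without them a later death cannot be called on or off treatment.

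A third tempting reading is that the primary composite loses the stroke survivor who later dies. It does not, because that patient was counted at the stroke. A death after admission with no earlier MI or stroke could be lost from the Medicare composite, but only if its death component uses the vital status file. Appendix A labels that component as inpatient mortality and then refers to the mortality sheet, which gives the vital status file for Medicare, so the text is ambiguous.

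Fourth, a reader might treat all 3,211 saxagliptin patients in the combined row as admissions and multiply by an assumed death rate. The documents do not give that split, and the counts are neither Medicare-only nor ITT. Censoring also removes person-time, so fewer counted deaths do not by themselves bias a hazard ratio.

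Finally, the carry-over to ITT is inferred, because the list is introduced for AT. It is the natural reading of a sentence that replaces named items only. If the sponsor meant otherwise, one sentence is still needed. Balance on baseline frailty, dementia and comorbidity is good, but it does not rule out different admission rates later.

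**Conclusion.** The point holds for one analysis: Medicare, ITT, all-cause mortality. There the plan, as worded, discards deaths that it has on record inside the 365-day window, and the reason given does not cover them. That the censoring is informative is plausible but is not shown by any figure in the documents. Its size and direction cannot be determined while Section 9 reports 7,208 and 3,211 patients in a row shared with SU switching. No bias in a hazard ratio has been demonstrated, and the AT primary analysis is not called into question. This concerns a secondary endpoint under the secondary follow-up scheme in one database, and it is worth correcting because the correction is cheap. The conclusion assumes that the ITT paragraph is read as Step 1 reads it, and that the vital status file records deaths irrespective of nursing home residence.

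**What to change.** - In 6.3.2, state that nursing home admission does not censor the Medicare ITT analysis of all-cause mortality. Follow-up there would still end at 365 days or at any other remaining reason on the list.
- Report the Medicare ITT composite without this censoring as a sensitivity analysis only. Note that MI and stroke may be under-captured after admission, and that the analysis is relevant only if the composite's death component uses the vital status file. Appendix A should say whether it does.
- Keep the censoring for all AT analyses and for Optum and MarketScan.
- In Section 9, report nursing home admission separately from SU switching, by arm and by database.
- In the same edit, reconcile the nursing home exclusion stated in 6.3.2 with the flowchart in 5.3.

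The cost is one additional Medicare run, a re-tabulation of existing censoring reasons, and a follow-up rule that differs for one endpoint and has to be explained in the report.
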